1. BACKGROUND AND PROTOCOL HISTORY

Background and Rationale

Maternal infection and sepsis are a priority to reduce maternal and neonatal deaths. Compared to postpartum hemorrhage and preeclampsia/eclampsia, maternal infection has received less attention as a major cause of maternal death; proportionally it accounts for increasing deaths. In addition, maternal infection significantly increases the risk of neonatal sepsis which is one of the leading causes of neonatal death in LICs. Drawing from our findings on azithromycin prophylaxis for cesarean delivery in the US and data from another preliminary trial in The Gambia, Africa, we proposed to evaluate the role of a single oral dose of azithromycin (plus usual care) to prevent maternal death or peripartum sepsis and intrapartum/neonatal death or sepsis in laboring women as well as the targeted sub-population of those at the highest risk for infection because they have prolonged labor (≥ 18 hours) and/or prolonged membrane rupture (≥ 8 hours).

Azithromycin is available as a generic agent with easy storage requirements. It has a bimodal half-life of up to 70 hours in the non-pregnant population. Although its pharmacokinetic characteristics are not as well studied in the pregnant population, it is commonly used during pregnancy for treatment of chlamydia and other infections. Azithromycin covers a broad spectrum of bacteria (including gram-positive cocci, genital ureaplasmas and mycoplasmas, and certain gram-negative bacilli and anaerobes) that are associated with maternal infections which are often polymicrobial (chorioamnionitis, endometritis, and perineal/cesarean wound infection) and sepsis. In addition to the aforementioned organisms which may play a role in neonatal infection, azithromycin also has activity against Group B streptococcus which is a major cause of neonatal sepsis in developed countries and may be implicated in LICs and low-resources settings as well. Therefore, a successful prophylaxis intervention is likely to reduce infections and death and may also reduce health care costs and need for prolonged antibiotic therapy to treat infections which may be associated with resistance.

Protocol History

The protocol in place at time of study implementation was finalized in July 2022 under Protocol version 1.6.

2. PURPOSE OF THE ANALYSES

This statistical analysis plan (SAP) contains detailed information about statistical analyses to be performed to assess the primary and secondary hypotheses outlined in the protocol including one formal interim analysis. The results of these analyses will be included in the study manuscript(s). Result of the formal interim analysis will be provided only to the Data and Safety Monitoring Board until study completion or early termination. Additional exploratory analyses may be performed to support further manuscript development. These analyses will not require an update to the SAP, but abbreviated analysis plans will be prepared prior to conducting those analyses.

3. STUDY OBJECTIVES AND OUTCOMES

3.1 Primary Hypothesis and Associated Outcomes

This study had two primary hypotheses, one with a maternal focus and one with a neonatal focus.

1. First, a single, prophylactic intrapartum oral dose of 2 g azithromycin given to women in labor in low and middle-income settings will reduce maternal death or sepsis.
2. Second, a single, prophylactic intrapartum oral dose of 2 g azithromycin given to women in labor in low and middle-income settings will reduce intrapartum/neonatal death or sepsis.

The primary outcomes are:

1. Maternal: Incidence of maternal death or sepsis within 6 weeks (42 days) post-delivery in intervention vs. placebo group.
2. Neonatal: Incidence of intrapartum/neonatal death or sepsis within 4 weeks (28 days) post-delivery in intervention vs. placebo group.

Maternal sepsis is a life-threatening condition defined as organ dysfunction resulting from suspected or confirmed infection that occurs post-randomization during labor or the postpartum period. This WHO definition, endorsed by multiple global health organizations, will be operationalized as suspected or confirmed infection based on the presence of fever ($>100.4^{\circ}\text{ F}/38^{\circ}\text{ C}$) or hypothermia ($<96.8^{\circ}\text{ F}/36^{\circ}\text{ C}$) plus one or more signs of mild to moderate organ dysfunction including tachycardia (≥120 bpm), low BP (systolic <90 mm Hg), tachypnea (>24 breaths/min), altered mental status/confusion, reduced urinary output (<500 cc over 24 hours), jaundice, or renal failure (>1.2 mg/dl). Components of peripartum infection which will be considered in making the diagnosis of suspected or confirmed infection include clinical chorioamnionitis, endometritis, wound infections (perineal or Cesarean), abdominal or pelvic abscess, mastitis/breast abscess or infection, pyelonephritis, pneumonia, and other bacterial infection.

Neonatal sepsis is defined as a newborn with proven or possible serious bacterial infection (pSBI) or pneumonia, meningitis, urinary tract infection, or omphalitis. Possible serious bacterial infection will be determined using WHO criteria of pSBI defined as severe chest in-drawing, fever (temperature $\geq 100.4^{\circ}\text{ F}/38^{\circ}\text{ C}$), hypothermia (temperature $<95.9^{\circ}\text{ F}/35.5^{\circ}\text{ C}$), no movement at all or movement only on stimulation, feeding poorly or not feeding at all, and/or convulsions. Clinical and laboratory signs of infection will also be considered in making the diagnosis of suspected or confirmed infection.

Only infections that occur post-randomization will count as study outcomes.

Masked adjudication of key infection outcomes will be implemented by the DCC and investigators during the trial to standardize and enhance the reproducibility of trial results. In addition to the above specified criteria, reported antibiotic treatment and culture status will also be considered as part of the adjudication process in making the diagnoses for both maternal and neonatal sepsis. Local site investigators will review and validate the diagnosis for all participants identified to have the primary outcomes applying pre-specified criteria. These reviews will be conducted masked to treatment group. If a case requires additional input and cannot be adjudicated locally, then it will

move to central adjudication where the study PIs will review the participant's information and make a final outcome determination. A random portion of the locally adjudicated cases will be selected for central review to ensure there are no systemic site difference in adjudication. This process will be coordinated by the DCC.

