2.5 Primary Outcomes

The primary outcomes are:

- Maternal: Incidence of maternal death or sepsis within 6 weeks (42 days) post-delivery in intervention vs. placebo group.
- Neonatal: Incidence of intrapartum/neonatal death or sepsis within 4 weeks (28 days) post-delivery in intervention vs. placebo group.

Maternal sepsis is a life-threatening condition defined as organ dysfunction resulting from suspected or confirmed infection that occurs post-randomization during labor or the postpartum period. This WHO definition, endorsed by multiple global health organizations, will be operationalized as suspected or confirmed infection based on the presence of fever ($>100.4^{\circ}\text{ F}/38^{\circ}\text{ C}$) or hypothermia ($<96.8^{\circ}\text{ F}/36^{\circ}\text{ C}$) plus one or more signs of mild to moderate organ dysfunction including tachycardia (≥120 bpm), low BP (systolic <90 mm Hg), tachypnea (>24 breaths/min), altered mental status/confusion, reduced urinary output (<500 ml over 24 hours), jaundice, or renal failure (>1.2 mg/dl).^{15,40,41,42} Components of peripartum infection which will be considered in making the diagnosis of suspected or confirmed infection include clinical chorioamnionitis, endometritis, wound infections (perineal or Cesarean), abdominal or pelvic abscess, mastitis/breast abscess or infection, pyelonephritis, pneumonia, and other bacterial infection as defined in Section 2.6 below.

Neonatal sepsis is defined as a newborn with proven or possible serious bacterial infection (pSBI) or pneumonia, or meningitis. Possible serious bacterial infection will be determined using WHO criteria of pSBI defined as severe chest in-drawing, fever (temperature $\geq 100.4^{\circ}\text{ F}/38.0^{\circ}\text{ C}$), hypothermia (temperature $<95.9^{\circ}\text{ F}/35.5^{\circ}\text{ C}$), no movement at all or movement only on stimulation, feeding poorly or not feeding at all, and/or convulsions.³³ Clinical and laboratory signs of infection will also be considered in making the diagnosis of suspected or confirmed infection.

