Centralized masked adjudication of key infection outcomes will be implemented by the DCC and investigators during the trial to standardize and enhance the reproducibility of trial results. In addition to the above specified criteria, reported antibiotic treatment and culture status will also be considered as part of the adjudication process in making the diagnoses for both maternal and neonatal sepsis. Local site investigators will review and validate the diagnosis for all participants identified to have the primary outcomes applying pre-specified criteria. These reviews will be conducted masked to treatment group. A second investigator from a different site will review the participant's information and make a final outcome determination. If this does not agree with the determination of the local site investigator, then the adjudicating investigator will discuss with the local investigator to reach a consensus, failing which the study PIs will make the final call. This process will be coordinated by the DCC.

The individual components of these primary outcomes are also of interest and will be analyzed.

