2.7 Other Neonatal Outcomes

- a. Other neonatal infections (e.g., eye infection, skin infection, omphalitis, urinary tract infection, respiratory rate ≥ 60 breaths/minute).
- b. Neonatal initial hospital length of stay, defined as time of delivery until initial discharge (time may vary by site).
- c. Neonatal readmission within 42 days of delivery.
- d. Neonatal admission to special care units.
- e. Neonatal unscheduled visit for care.
- f. Neonatal death due to sepsis using the Global Network algorithm for causes of death.
- g. Pyloric stenosis within 42 days of delivery, defined as clinical suspicion based on severe vomiting leading to death, surgical intervention (pyloromyotomy) as verified from medical records, or radiological confirmation.

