 - Time from drug administration until initial discharge after delivery (time may vary by site).
 - Maternal readmission within 42 days of delivery.
 - Maternal admission to special care units.
 - Maternal unscheduled visit for care.
 - Maternal GI symptoms including nausea, vomiting, and diarrhea and other reported side effects.
 - Maternal death due to sepsis using the Global Network algorithm of causes of death.
- Other Neonatal Outcomes
 - Other neonatal infections (e.g. eye infection, skin infection, omphalitis, urinary tract infection, respiratory rate ≥ 60 breaths/minute)

- Neonatal initial hospital length of stay, defined as time of delivery until initial discharge (time may vary by site).
- Neonatal readmission within 42 days of delivery.
- Neonatal admission to special care units.
- Neonatal unscheduled visit for care.
- Neonatal death due to sepsis using the Global Network algorithm for causes of death.
- Pyloric stenosis within 42 days of delivery, defined as clinical suspicion based on severe vomiting leading to death, surgical intervention (pyloromyotomy) as verified from medical records, or radiological confirmation.

Detailed definitions for deriving the associated variables are included in Section 9.

Type of culture positive infections, antimicrobial resistance and maternal and infant microbiome diversity were compared in an ancillary study and the associated analyses described in a separate analysis plan.

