Maternal GI symptoms including nausea, vomiting, and diarrhea and other reported side effects.	Binary	
The outcome will be defined as “Yes” if vomiting or diarrhea are reported after delivery on AZ03 or AZ05a; an unscheduled care visit for nausea, vomiting, or diarrhea is reported on AZ05a; or an unscheduled care visit for nausea, vomiting and/or diarrhea is reported on AZ07; or a mechanistically-related AE is reported (e.g. abdominal pain); and “No” otherwise. The outcome will only be missing for mothers that are lost to follow-up prior to completion of a Day 7 visit and had no symptoms or side effects reported prior to becoming LTF.
 
Analysis population(s): As Treated

Neonatal Other Infections	Binary	
The event will be defined as “Yes” if any infection is reported that does not qualify for sepsis prior to day 28 and “No” otherwise. Other neonatal infections include eye infection with swelling and drainage, skin infection with 10 or more pustules or bullae, omphalitis, urinary tract infection, pyelonephritis or kidney infection, pneumonia or lung infection, meningitis, other infection documented in clinical record or respiratory rate ≥ 60. The outcome will only be missing for infants that are lost to follow-up prior to completion of a Day 7 visit and neonatal deaths prior to 7 days that do not qualify for sepsis or other infections.
 
Analysis population(s): ITT (all-comer and high risk)

Variable	Type	Definition
Neonatal initial hospital length of stay	Ordinal	Defined as the date/time of initial discharge reported on AZ04 or AZ08 – date/time of delivery reported on AZ03 Analysis population(s): ITT (all-comer and high risk)
Neonatal readmissions within 42 days of delivery	Binary	Only defined for live births who were initially discharged from the hospital following delivery as documented on AZ04 or AZ08 (i.e. stillbirths or infants that die during the initial hospitalization for delivery will be excluded from the numerator and denominator). The outcome will be defined as “Yes” if the location of any subsequent study visit on AZ05b is In-patient (hospitalized), or if there is an AZ08 form where the infant is noted as admitted or has a non-missing admission date; and “No” otherwise. The outcome will only be missing for infants that are lost to follow-up prior to completion of a Day 7 visit and had no readmission reported prior to becoming LTF. Analysis population(s): ITT (all-comer and high risk)

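### SAP 3.1 counts urinary tract infection and omphalitis as neonatal sepsis and protocol 2.5 does not, so a formally tested primary outcome has two written definitions

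*Combined protocol and SAP*

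**What the plan says.** The texts compared here are all current: the protocol at version 1.6 and the SAP at version 2.0, which names version 1.6 as its protocol.

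- **SAP 3.1**, primary outcomes: "Neonatal sepsis is defined as a newborn with proven or possible serious bacterial infection (pSBI) or pneumonia, meningitis, urinary tract infection, or omphalitis".
- **Protocol 2.5**, primary outcomes: "Neonatal sepsis is defined as a newborn with proven or possible serious bacterial infection (pSBI) or pneumonia, or meningitis".
- **Protocol 2.7**, a separate secondary outcome: "Other neonatal infections (e.g., eye infection, skin infection, omphalitis, urinary tract infection".
- **SAP 3.2**, the same secondary outcome: "Other neonatal infections (e.g. eye infection, skin infection, omphalitis, urinary tract infection". This section then points onward: "Detailed definitions for deriving the associated variables are included in Section 9".
- **SAP 9.2**, the row for neonatal other infections, applies if "any infection is reported that does not qualify for sepsis prior to day 28". Its list includes "omphalitis, urinary tract infection, pyelonephritis or kidney infection, pneumonia or lung infection, meningitis".
- **SAP 9.2**, the row for neonatal sepsis, names no infections and leaves the details to the adjudication plan. SAP 4.4 says that plan also holds the programmed algorithm.
- **SAP 9.3** tests each of the two primary hypotheses formally at alpha 0.05.
- **SAP 12**, reserved for changes from the protocol's analyses, is a heading with no text under it.

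**The concern.** An infant whose only qualifying event is a UTI or omphalitis is a primary-outcome event under SAP 3.1 and a non-event under protocol 2.5. The same infant also moves between outcomes, because SAP 9.2 restricts other infections to those that do not qualify as sepsis. The choice of list therefore affects the event count and relative risk of a formally tested primary outcome, the neonatal sepsis component, and a secondary outcome.

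If the conflict is still open when the data are unmasked, settling it means choosing the content of a primary endpoint with the results in view. No inflation of the Type I error is claimed from the wording alone.

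**Working it through.** **1. Do the texts conflict?**

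| Place | pSBI, pneumonia, meningitis | UTI, omphalitis |
|---|---|---|
| SAP 3.1 | sepsis | sepsis |
| Protocol 2.5 | sepsis | not listed |
| Protocol 2.7 | not listed | other infection |
| SAP 3.2 | not listed | other infection |
| SAP 9.2, other infections | pneumonia and meningitis listed, if not qualifying as sepsis | listed, if not qualifying as sepsis |

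The first four rows establish the conflict. The last row cannot settle it: it is a residual category that also names pneumonia and meningitis, which are sepsis under both definitions, so being named there does not show exclusion from sepsis. SAP 3.1 otherwise matches protocol 2.5 on the pSBI signs, including the 38 °C fever threshold, and on leaving out eye and skin infections. That pattern suggests an incomplete update, but this is an inference.

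**2. Who is affected?** An infant with UTI or omphalitis plus a pSBI sign, a proven serious bacterial infection, pneumonia or meningitis is sepsis under both texts. Only isolated cases change class. Both documents also let further information inform the diagnosis (in protocol 2.5, "reported antibiotic treatment and culture status will also be considered as part of the adjudication process"), which may narrow the group further.

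**3. How large could the effect be?** The documents give no rate of isolated UTI or omphalitis. The rate x is therefore an assumption, set at 0.5, 1 and 2 percentage points for illustration. These values are not bounds.

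Inputs from SAP 6.1: 34,000 women at 1:1 allocation; 3% loss (upper end of the stated 2% to 3%); baseline risk 8%; Asia 50% and sub-Saharan Africa 37.5% of enrolment; regional alpha 0.025. Multiple births are ignored. Evaluable per arm:

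- overall: 17,000 × 0.97 = 16,490
- Asia: 16,490 × 0.50 = 8,245
- Africa: 16,490 × 0.375 ≈ 6,184

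Formula (two proportions, pooled variance under the null, two-sided, p̄ = (p1 + p2)/2):

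n = [z(1−α/2)·√(2p̄(1−p̄)) + z(power)·√(p1(1−p1) + p2(1−p2))]² / (p1 − p2)²

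This reproduces the plan's own 90% power figures per arm: 5,483 (8% vs 6.4%, alpha 0.05), 6,477 (8% vs 6.4%, alpha 0.025) and 4,038 (8% vs 6%, alpha 0.025). Solving the same formula for power at the planned size with x = 0 gives 99.99% overall, 95.9% in Asia and 98.3% in Africa.

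SAP 6.1 does not say whether its 8% includes these cases, so both directions are shown. Overall and Asia use a 20% reduction, Africa 25%.

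*Direction 1: cases are added to the 8% and the drug has no effect on them.* RR = (0.064 + x)/(0.08 + x) for the 20% scenario.

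| x | RR (20% scenario) | Power overall | Asia | Africa |
|---|---|---|---|---|
| 0.005 | 0.069/0.085 = 0.812 | 99.98% | 94.66% | 97.63% |
| 0.010 | 0.074/0.090 = 0.822 | 99.96% | 93.37% | 96.85% |
| 0.020 | 0.084/0.100 = 0.840 | 99.89% | 90.55% | 95.01% |

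In the 25% Africa scenario, RR = (0.06 + x)/(0.08 + x), which runs from 0.765 to 0.800.

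*Direction 2: cases are already in the 8% and the narrower list removes them, with the relative effect unchanged.*

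| x | Placebo risk | Power overall | Asia | Africa |
|---|---|---|---|---|
| 0.005 | 7.5% | 99.97% | 94.50% | 97.56% |
| 0.010 | 7.0% | 99.95% | 92.77% | 96.55% |
| 0.020 | 6.0% | 99.79% | 87.86% | 93.31% |

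In direction 2, power in Asia reaches 90% at x = 1.62 points (1.68 with 2% loss). If added cases responded equally to the drug, the RR would stay at 0.80 and power in Asia would rise to between 96.9% and 98.8%.

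In events, x of 0.5 to 2 points is 16,490 × 0.005 ≈ 82 to 16,490 × 0.02 ≈ 330 infants in the placebo arm.

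**The case against.** The strongest reply is that SAP 3.1 may not be the operative definition. SAP 9.2 sends neonatal sepsis to the adjudication plan, and SAP 2 says the SAP serves the hypotheses set out in the protocol. The wider list could be a stale sentence with no effect on any programmed endpoint. That is possible, and these documents cannot exclude it. It does not remove the conflict: adjudicators apply pre-specified criteria, and the written criteria are what differ. Even if the algorithm follows the protocol, the SAP would misstate the endpoint that was analysed.

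Two further points stand. SAP 9.2 is weak evidence, and the case does not need it. The numerical range is also speculative and its upper end may be generous: the low end of the planned risk assumes about 4% non-fatal sepsis, so removing 2 points would make half of that (2/4) isolated UTI or omphalitis, and the 1.6-point crossing in Asia would be 40% (1.6/4). That crossing concerns a secondary regional test, made only if the interaction has p below 0.1. SAP 6.1 makes its 90% claim conditional on a baseline of at least 8%, so the crossing is a sensitivity and not a failed claim.

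**Conclusion.** The concern holds. The current protocol and the current SAP define a component of a formally tested primary outcome differently, the SAP is also inconsistent between 3.1 and 3.2, and no departure is declared. Following SAP 3.1 as written would count events that the protocol excludes.

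The true size cannot be found from the documents. On the assumed 0.5 to 2 points of isolated cases, the main consequence is a shift in the estimated effect (0.80 to between 0.81 and 0.84 if the drug does not act on the added cases) and a different event count. Overall power remains about 99.8% or higher in both directions. The defect is an ambiguous endpoint and should be resolved before unmasking.

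**What to change.** Before unmasking:

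1. Replace the list in SAP 3.1 with that of protocol 2.5, leaving out UTI and omphalitis. If the wider list is intended, record and justify the departure in SAP 12 and take both conditions out of the other-infection lists in SAP 3.2 and 9.2.
2. Confirm in writing that the adjudication plan and the endpoint program use the same list as the SAP.
3. Make that decision masked, by staff who have not seen interim results. SAP 7.6 already keeps those statisticians out of decisions in later masked reviews.

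The cost is one sentence in SAP 3.1 (or one entry in section 12 and edits to two lists) and a masked check of the algorithm. No new data are needed.

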3.2 Secondary Aims and Associated Outcomes

The single dose of intrapartum azithromycin prophylaxis (2 g) will be compared to placebo to accomplish the following secondary aims:

Main Secondary Aim for Women at High Risk for Infection Cohort:

- a. To evaluate whether the risk of maternal death or sepsis differs among laboring women with and without high-risk for infection (high risk is defined as women with prolonged labor [≥ 18 hours] and/or prolonged membrane rupture [≥ 8 hours]).

Other Secondary Specific Aims:

- b. To evaluate the effectiveness in reducing the risk of individual components of the primary composite endpoints (i.e., maternal death, maternal sepsis, intrapartum/neonatal death, neonatal sepsis including specifically all-cause neonatal deaths and neonatal deaths due to sepsis).
- c. To evaluate the effectiveness on the risk of intrapartum/neonatal death or sepsis in infants of laboring women at high-risk for infection because of prolonged labor (≥ 18 hours) and/or prolonged membrane rupture (≥ 8 hours).
- d. To evaluate the effectiveness on the risk of maternal infections including clinical chorioamnionitis, endometritis, wound infections (perineal or subsequent cesarean), abdominal or pelvic abscess, mastitis/breast abscess, pyelonephritis and pneumonia in all laboring women as well as in those at high-risk for infection.
- e. To evaluate the effectiveness in reducing the use of subsequent maternal antibiotic therapy from randomization to 42 days postpartum for any reason in all laboring women as well as in those at high-risk for infection.
- f. To compare the use of health care resources. Use of health care resources will be measured in terms of maternal and neonatal duration of hospital stay, unscheduled visits, readmissions, and admission to special care units/intensive care units in all laboring women and newborns as well as in those at high-risk for infection.
- g. To assess maternal GI symptoms (e.g., nausea, vomiting, and diarrhea) and other reported side effects, as well as infant pyloric stenosis and type of culture positive infections (antimicrobial resistance and maternal and infant microbiome diversity are compared in an ancillary study).
- h. To determine whether the effect on each of the primary outcomes differs by region (Africa, Latin America or Asia), any other antibiotic use during labor, and mode of delivery (cesarean or vaginal). Note that antibiotic use will not include use to treat any infections diagnosed after randomization as those will be outcomes.

These secondary aims will be assessed using the following outcomes.

- The individual components of the primary outcomes (i.e., maternal death, maternal sepsis, maternal death due to sepsis, intrapartum/neonatal death, neonatal sepsis including specifically all-cause neonatal deaths and neonatal deaths due to sepsis)

- Other Maternal Outcomes
 - Chorioamnionitis: Fever ($>100.4^{\circ}\text{F}/38^{\circ}\text{C}$) in addition to one or more of the following: fetal tachycardia ≥ 160 bpm, maternal tachycardia > 100 bpm, tender uterus between contractions, or purulent/foul discharge from uterus **prior** to delivery.
 - Endometritis: Fever ($>100.4^{\circ}\text{F}/38^{\circ}\text{C}$) in addition to one or more of maternal tachycardia > 100 bpm, tender uterine fundus, or purulent/foul discharge from uterus **after** delivery.
 - Wound infection refers to purulent infection (superficial or deep infection including necrotizing fasciitis) of a perineal wound or wound of a cesarean with or without fever; In the absence of purulence, a wound infection requires presence of fever ($>100.4^{\circ}\text{F}/38^{\circ}\text{C}$) and at least one of the following signs of local infection: pain or tenderness, swelling, heat, or redness around the incision/laceration.
 - Other infections:
 - Abdominopelvic abscess is evidence of pus in the abdomen or pelvis noted during open surgery, interventional aspiration or imaging;
 - Mastitis/breast abscess or infection refers to fever ($>100.4^{\circ}\text{F}/38^{\circ}\text{C}$) and one or more of the following: breast pain, swelling, warmth, redness, or purulent drainage (for breast abscess).
 - Pyelonephritis refers to fever ($>100.4^{\circ}\text{F}/38^{\circ}\text{C}$) and one or more of the following: urinalysis/dip suggestive of infection or costovertebral angle tenderness or confirmatory urine culture.
 - Pneumonia refers to fever ($>100.4^{\circ}\text{F}/38^{\circ}\text{C}$) and clinical symptoms suggestive of lung infection including cough and/or tachypnea or radiological confirmation.
 - Use of subsequent maternal antibiotic therapy after randomization to 42 days postpartum for any reason.
 - Time from drug administration until initial discharge after delivery (time may vary by site).
 - Maternal readmission within 42 days of delivery.
 - Maternal admission to special care units.
 - Maternal unscheduled visit for care.
 - Maternal GI symptoms including nausea, vomiting, and diarrhea and other reported side effects.
 - Maternal death due to sepsis using the Global Network algorithm of causes of death.
- Other Neonatal Outcomes
 - Other neonatal infections (e.g. eye infection, skin infection, omphalitis, urinary tract infection, respiratory rate ≥ 60 breaths/minute)

- Neonatal initial hospital length of stay, defined as time of delivery until initial discharge (time may vary by site).
- Neonatal readmission within 42 days of delivery.
- Neonatal admission to special care units.
- Neonatal unscheduled visit for care.
- Neonatal death due to sepsis using the Global Network algorithm for causes of death.
- Pyloric stenosis within 42 days of delivery, defined as clinical suspicion based on severe vomiting leading to death, surgical intervention (pyloromyotomy) as verified from medical records, or radiological confirmation.

Detailed definitions for deriving the associated variables are included in Section 9.

Type of culture positive infections, antimicrobial resistance and maternal and infant microbiome diversity were compared in an ancillary study and the associated analyses described in a separate analysis plan.

